Dose escalation and de-escalation in Phase 1 will follow the BOPIN design algorithm (Yuan and Liu 2016). Given the target DLT rate of 33% for INCB001158 in combination with daratumumab SC, the dose escalation and de-escalation rules are shown in Table 11. The BOPIN design also includes an elimination rule. When ≥ 3 participants have been treated, if the probability that the estimated toxicity rate that is above the target DLT rate is $> 95\%$ at a certain dose level, then this dose level and higher dose levels are assumed to be too toxic and will be eliminated. If the lowest dose level is eliminated, then the whole dose escalation will be terminated. Table 11 (in the bottom row) provides the elimination rules. Based on this algorithm, a minimum of 3 evaluable participants and a maximum of 9 evaluable participants will be enrolled at each tested dose level. The dose escalation will continue, based on the rules in Table 11, until at least 1 of the following occurs:

- Enrollment of additional participants at a dose level that already has 9 evaluable participants.
- Dose escalation to a dose level that has already been eliminated.
- Dose escalation above 100 mg BID.

At that point, the dose escalation will be stopped.

Table 11: Dose Escalation, De-Escalation, and Elimination Boundaries for Target DLT Rate of 33% in Phase 1

Action	Number of Evaluable Participants Treated at the Current Dose								
	1	2	3	4	5	6	7	8	9 ^a
Escalate if # of DLTs \leq	0	0	0	1	1	1	1	2	2
De-escalate if # of DLTs \geq	1	1	2	2	2	3	3	4	4
Elimination if # of DLTs \geq	N/A	N/A	3	3	4	4	5	5	6

DLT = dose-limiting toxicity; N/A = not applicable.

^a If 9 evaluable participants are enrolled at a dose level, and 3 of those participants experience a DLT, then the medical monitor and the investigators will review the entirety of the data and decide whether to escalate the dose level, de-escalate the dose level, or stop at that dose level.

The INCB001158 dose will be escalated using an open-label BOPIN design and a PAD or the MTD will be determined, or the maximum dose of INCB001158 (100 mg BID) will be reached.

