A PAD of INCB001158 is defined as a dose that achieves a C_{min} of INCB001158 at steady state of $\geq 1 \mu\text{M}$ that is equivalent to the IC_{90} for arginase 1. The MTD is the maximum tolerated or tested dose of INCB001158, such that fewer than 33% of the participants receiving the combination experience a DLT during the first 28 days on study drug. After the dose escalation is completed, one of the INCB001158 dose levels that is pharmacologically active and tolerable in combination with daratumumab SC (ie, MTD or lower), will be selected as the RP2D.

Dose interruptions and/or modifications may be implemented based on toxicity. Dose modifications should not be made during the DLT observation period without discussion with the medical monitor. Intraparticipant dose escalation is not permitted. At the discretion of the sponsor, up to 6 additional "backfill" participants may be enrolled at any tolerable dose level to further investigate safety, efficacy [REDACTED].

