6. STUDY TREATMENT

6.1. Study Treatment(s) Administered

In this Protocol, the term "study drug" refers to INCB001158 only, and "study treatment" refers to INCB001158, daratumumab SC, or the combination of INCB001158 and daratumumab SC.

[Table 14](#) presents the study treatment information.

Table 14: Study Treatment Information

Study treatment name:	INCB001158	Daratumumab SC
Dosage formulation:	25 mg and 100 mg tablets	120 mg/mL daratumumab + 20 µg/mL rHuPH20 solution
Unit dose strength(s) /dosage level(s):	50 mg BID 75 mg BID 100 mg BID	1800 mg
Route of administration:	PO	SC
Administration instructions:	Administered PO BID, in the morning and evening, approximately 12 hours apart, without respect to food (see Appendix B).	Administered SC by manual push over 3-5 minutes (see Appendix C and daratumumab IPPI).
Packaging and labeling:	INCB001158 will be provided as 25 mg and 100 mg tablets packaged in bottles, respectively. No preparation is required. Each bottle will be labeled as required per country requirement.	Daratumumab SC will be provided in glass vials containing daratumumab at a concentration of 120 mg/mL and rHuPH20 at a concentration of 2000 U/mL (~20 µg/mL). It will be supplied to the site/pharmacy as open-label supply. Each vial will be labeled as required per country requirement.
Storage:	Ambient conditions 15°C to 30°C (59°F to 86°F).	Under refrigeration 2°C-8°C (36°F-46°F). Protect from light.

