6.6.1. Definition of a Dose-Limiting Toxicity

A DLT will be defined as the occurrence of any of the toxicities in [Table 16](#) occurring from the start of study treatment up to and including Day 28, except those with a clear alternative explanation (eg, disease progression) or transient (≤ 72 hours) abnormal laboratory values

without associated clinically significant signs or symptoms based on investigator determination. All DLTs will be assessed for severity by the investigator using CTCAE v5 criteria. Participants who receive at least 42 of 56 ($\geq 75\%$) doses of study drug at the level assigned or have a DLT will be considered evaluable for determining tolerability of the dose. Participants who do not meet these criteria may be replaced to obtain sufficient evaluable participants to be able to assess that dose level using the BOIN design, as outlined in [Table 11](#).

Clear evidence of urea cycle inhibition (eg, an increase in fasting urinary orotic acid to $> 10 \times \text{ULN}$ or any orotic acid value of $> 40 \times \text{ULN}$, accompanied by plasma ammonia elevation $\geq 2 \times \text{ULN}$ and $\geq 2 \times \text{baseline}$, or symptomatic hyperammonemia) would be considered a dose-limiting event and will be treated the same as a DLT with regard to the dose-escalation rules and definition of the MTD described in Section [4.1.1](#). Refer to the INCB001158 [IB](#) for an explanation of the orotic acid thresholds.

Individual participant dose reductions may be made based on events observed at any time during treatment with study drug; however, for the purposes of dose level escalation/de-escalation, expanding a dose level, and for determining the MTD of INCB001158, decisions will be made based on events that are observed from the first day of study drug administration through and including the final day of Cycle 1 (Day 28). A lower MTD may subsequently be determined based on relevant toxicities that become evident after Day 28.

Table 16: Definition of a Dose-Limiting Toxicity

Toxicity	Definition

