6.7.1. Dose Modifications of INCB001158

For participants in Phase 1, dose reductions of INCB001158 will be permitted during the first 28 days only if a participant experiences a DLT or a toxicity that may herald a DLT. If a participant experiences a DLT, treatment continuation at a lower dose of INCB001158 will be permitted as long as the toxicity has returned to \leq Grade 1 or baseline within 28 days. When INCB001158 is held or discontinued, daratumumab SC may be continued, at the investigator's discretion. Upon recovery, participants may restart at 1 INCB001158 dose level lower. Participants who do not recover within 28 days will not be eligible for resumption of study treatment without approval from the medical monitor. See also [Table 17](#).

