10.2. Populations for Analysis

[Table 27](#) presents the populations for analysis.

Table 27: Populations for Analysis

Population	Description
Enrolled	All participants who sign the ICF.
FAS	All participants enrolled in the study who received at least 1 dose of study treatment (INCB001158 or daratumumab SC). Participants will be analyzed according to the treatment that they were assigned to. The FAS will be used for the summary of demographics, baseline characteristics, and disposition.
IMWG response evaluable	All participants enrolled in the study who have received at least 1 dose of study treatment (INCB001158 or daratumumab SC), completed a baseline disease assessment, and meet at least 1 of the following criteria: 
 • ≥ 1 postbaseline disease assessment • Been on the study for a minimum of 35 days of follow-up • Discontinued from treatment
DLT evaluable	All participants who receive at least 42 of 56 doses for the 28-day cycle regimen (representing $\geq 75\%$ of the dose planned) of INCB001158 at the level assigned or who have a DLT.

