5.3.2. Full Analysis Set

The FAS will include all participants who received at least 1 dose of INCB001158 or daratumumab SC. Participants will be analyzed according to the treatment to which they have been initially assigned.

This population will be used for summaries of demographics, baseline characteristics, participant disposition, safety, and exposure.

5.3.3. DLT Evaluable Population for Phase 1

The DLT evaluable population includes participants who have received at least 42 of 56 doses for the 28-day cycle regimen (representing $\geq 75\%$ of the dose planned) of INCB001158 or who have a DLT.

Note that the DLT evaluable population will exclude participants in the randomized part (Phase 2) of the study.

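### SAP 5.3.3 leaves out the protocol's assigned-level condition from the DLT evaluable population without declaring it, which can inflate the reported evaluable count

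*SAP*

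**What the plan says.** The protocol gives the evaluability rule twice. Section 6.6.1, which governs dose decisions, says that participants with at least 42 of 56 (75% or more) "doses of study drug at the level assigned or have a DLT will be considered evaluable for determining tolerability of the dose". Table 27 in section 10.2 repeats the 42-of-56 count, with a parenthesis equating it to at least 75% of the planned dose, and completes it with "of INCB001158 at the level assigned or who have a DLT".

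SAP 5.3.3 reads: "The DLT evaluable population includes participants who have received at least 42 of 56 doses for the 28-day cycle regimen". It keeps the 75% parenthesis and the alternative of having a DLT, but the reference to the assigned level is gone. SAP 2.1 says that the SAP is based on Protocol Amendment 3. SAP 10.1, which records departures from the protocol, mentions only the dropped efficacy analyses.

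Protocol 6.7.1 says that INCB001158 dose reductions in Phase 1 "will be permitted during the first 28 days only if a participant experiences a DLT or a toxicity that may herald a DLT".

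On the partner drug, Protocol 6.1 says that the term study drug "refers to INCB001158 only". The escalation rule in Protocol 4.1.1 begins "Given the target DLT rate of 33% for INCB001158 in combination with daratumumab SC", and the same section defines the MTD so that "fewer than 33% of the participants receiving the combination experience a DLT during the first 28 days on study drug".

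**The concern.** The DLT evaluable population is the natural denominator for any statement about tolerability at a dose level. Without the assigned-level condition, it can include people who spent much of the DLT window on a lower dose than the one under which they are counted. They would have been reduced because of toxicity and would still appear as DLT-free at the original level, so the error runs in one direction, towards tolerability.

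A reader of the study report would have no warning that the count may differ from the one used during escalation. Efficacy is confined to listings (SAP 7.1 and 10.1), so safety is the main content of the report.

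A second gap is shared by both documents. The DLT target and the MTD describe the combination, but evaluability is judged on INCB001158 doses alone.

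**Working it through.** **1. The threshold.** Twice-daily dosing for 28 days gives 2 × 28 = 56 doses, and 42/56 = 75%. Protocol and SAP agree on this figure.

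**2. The two rules side by side, for a Phase 1 participant.**

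| INCB001158 exposure and outcome in the window | Protocol 6.6.1 and Table 27 | SAP 5.3.3 |
|---|---|---|
| At least 42 doses at the assigned level, no DLT | Evaluable, DLT-free | Evaluable, DLT-free |
| Fewer than 42 doses in total, no DLT | Not evaluable | Not evaluable |
| Any exposure, DLT | Evaluable, DLT | Evaluable, DLT |
| At least 42 in total, fewer than 42 at the assigned level, no DLT | Not evaluable | Evaluable, DLT-free |

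Only the last row differs. Protocol 6.7.1 makes it reachable, because it permits a reduction in the window for a toxicity that only heralds a DLT. The reduction must take effect before the 42nd full-level dose, which falls at 42/2 = 21 days if nothing is missed.

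**3. Whether the 75% parenthesis closes the gap.** Dose levels are 50, 75 and 100 mg BID (Protocol Table 10).

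- Read as a count, it only restates 42/56.
- Read as milligrams, it excludes some reduced participants. Forty-two doses all one level lower give 42 × 75/(56 × 100) = 56.25% at the 100 mg level and 42 × 50/(56 × 75) = 50.0% at the 75 mg level.
- It does not exclude a participant reduced part-way. Take a hypothetical reduction after Day 14: 28 doses at the assigned level, then 28 one level lower. At the 100 mg level this is (28 × 100 + 28 × 75)/(56 × 100) = 4900/5600 = 87.5% of planned mg. At the 75 mg level it is (28 × 75 + 28 × 50)/(56 × 75) = 3500/4200 = 83.3%. Both pass 75% with only 28 doses at the assigned level, against the 42 that the protocol requires.

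**4. Effect on a rate.** With m DLTs among n evaluable participants under the protocol and k extra DLT-free participants under the SAP, m/n becomes m/(n + k). For example, 1/3 = 33.3% becomes 1/4 = 25.0% with k = 1, and 2/6 = 33.3% becomes 2/8 = 25.0% with k = 2. The value of k is not in the documents and may be zero.

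**5. Which outputs can change.**

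- SAP Appendix A Table 1.1.2 and Listing 2.3.1 (both titled Analysis Populations) can change in count and membership. The table shells are not in the documents; I assume that both show the DLT evaluable population, which is one of the three defined in SAP 5.3.
- Listing 2.7.2.1 cannot change. SAP 8.2.2 restricts it to participants with DLTs, who qualify under either rule.
- Appendix A plans no DLT rate or DLT summary table.

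**6. Timing.** Protocol Appendix F records that enrollment had ended by Amendment 3 (01 DEC 2021). SAP Table 7 lists one version, dated 19 APR 2022.

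**7. Daratumumab.** Cycle 1 contains 4 weekly doses. The minimum that either document requires for DLT evaluability is 0 of 4. Protocol 6.7.4 allows INCB001158 to continue while daratumumab is held, with the medical monitor's approval, and missed daratumumab doses are not made up. A participant can therefore reach 42 INCB001158 doses with incomplete daratumumab and no DLT, and count as DLT-free for the combination.

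**The case against.** The strongest reply is that the omission has no practical effect, and much of that stands.

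- *Escalation.* A reader might infer from Protocol Table 11 that the SAP wording could turn a stay decision (1 DLT in 3) into an escalate decision (1 in 4). The look-up is right, but the inference fails. Table 11 was applied with the protocol's rule, which has the assigned-level condition, and the SAP was written after enrollment ended.
- *Primary safety result.* A reader might infer that the Phase 1 primary result is biased. The documents do not support this. The primary endpoint is the frequency, duration and severity of AEs (SAP Table 1), summarised on the FAS (SAP 5.3.2 and 8.2.4), which this wording does not touch.
- *Breadth.* Not everyone who missed the assigned dose is miscounted. Those below 42 doses without a DLT are excluded under both rules, and those reduced because of a DLT count as DLTs. Protocol 4.1.1 also calls for discussion with the medical monitor before any dose change in the window.
- *The parenthesis.* It might be called a safeguard. This does not stand: Table 27 carries the same parenthesis together with the missing phrase, so it glosses 42/56 and does not replace the condition. Step 3 shows that the milligram reading also fails.
- *Daratumumab.* It is a fixed-dose partner, and INCB001158 is the escalated agent. Many reasons to hold daratumumab in Protocol 6.7.4 also meet the DLT definition in Table 16, and Protocol 5.5 allows replacement of participants who withdraw from study treatment. SAP and protocol agree here, so there is no conflict between them. A reader might infer that the selected dose is unsound, or that a minimum number of daratumumab doses should be imposed. The documents show no affected participant and contain no basis for a cut-off.

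**Conclusion.** SAP 5.3.3 departs from Protocol 6.6.1 and Table 27 by omitting the assigned-level condition, and SAP 10.1 does not declare it. Followed as written, it counts as evaluable and DLT-free a participant whom the protocol treats as non-evaluable. The effect is confined to the DLT evaluable count by dose level and to any DLT rate that a reader or author derives from it. Each affected participant adds one to that denominator, always in the direction of a lower rate.

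The number affected is unknown, so a mismatch with the escalation denominator is possible but not shown. No dose decision and no row of the DLT listing depends on the SAP wording.

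The absence of any daratumumab exposure requirement is a separate limitation of the protocol's own rule. It affects how a DLT rate for the combination should be read. The documents give no basis for attaching a size to it.

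**What to change.** Restore *at the level assigned* in SAP 5.3.3 so that it matches Protocol 6.6.1 and Table 27. If the wider population is intended, declare and justify it in SAP 10.1. With the words restored, it no longer matters whether the 75% is read as a count or as milligrams, since 42 doses at the assigned level are 75% either way.

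As a descriptive addition only, show for each DLT evaluable participant the Cycle 1 exposure to INCB001158, by dose level, and to daratumumab. The data are already planned for Listings 2.5.1 and 2.5.3. No participant needs to be reclassified for past decisions, and no exposure cut-off for daratumumab needs to be introduced.

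The cost is four words in the SAP and a few columns in a listing, with no new data collection.

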6. BASELINE, EXPOSURE, AND DISPOSITION

[Appendix A](#) provides a list of data displays. Sample data displays are included in a separate document.

All summaries will be presented by dose level for Phase 1 and by treatment group for Phase 2.

6.1. Demographics, Baseline Characteristics, and Disease History

6.1.1. Demographics and Baseline Characteristics

The following demographics and baseline characteristics will be summarized for the FAS: age, sex, race, ethnicity, weight, and height.

6.1.2. Baseline Disease Characteristics and Disease History

The following baseline disease characteristics and disease history will be summarized for the FAS: ECOG performance status, time since diagnosis, Durie Salmon stage of initial diagnosis, R-ISS stage at initial diagnosis, Durie Salmon stage of current diagnosis, R-ISS stage at current diagnosis, and current myeloma type.

Time since diagnosis will be calculated as follows:

Time since diagnosis (years) = (Day 1 date – date of diagnosis + 1) / 365.25.

6.1.3. Prior Therapy

The number of prior therapy regimens for the disease under study will be summarized for all participants in the FAS. The component drugs of prior therapy regimens will be coded using the WHO Drug Dictionary. The number and percentage of participants who received each drug will be summarized by WHO drug class and WHO drug preferred term. The regimen name, component drugs, start and stop dates, purpose of the regimen, best response, reason for discontinuation, and date of relapse/progression will be listed.

The number of participants who received prior radiation will be summarized for the FAS. The radiotherapy type, body site, and start and stop dates will be listed.

The number of participants who had prior surgery or surgical procedure for the malignancies under study will be summarized for the FAS. The date and description of the surgery/procedure will be listed.

6.1.4. Medical History

For participants in the FAS, medical history will be summarized. This summary will include the number and percentage of participants with medical history events for each body system/organ class as documented on the eCRF.

6.2. Disposition of Participants

The number and percentage of participants who were screened, who failed screening, who were enrolled, who were treated, who were ongoing with study treatment, who completed study treatment, who discontinued study treatment with a primary reason for discontinuation, who were still in the study, who completed the study, and who withdrew from the study with a primary reason for withdrawal will be summarized for the FAS. The number of participants enrolled by country and site will also be provided.

6.3. Protocol Deviations

Protocol deviations recorded on the eCRF will be listed.

6.4. Exposure

6.4.1. Exposure to INCB001158

For participants in the Phase 1 and Phase 2 combined FAS, exposure to INCB001158 will be summarized descriptively as the following using information entered on the Dose INCB001158 eCRF:

- **Total actual dose (mg):** total actual dose taken of INCB001158.
- **Duration of treatment (days):** date of last dose of INCB001158 – date of first dose of INCB001158 + 1.
- **Average daily dose (mg):** total actual INCB001158 dose taken (mg) divided by the duration of treatment with INCB001158 (days).

6.4.2. Exposure to Daratumumab SC

For participants in the Phase 1 and Phase 2 combined FAS, exposure to daratumumab SC will be summarized descriptively as the following using information entered on the Daratumumab Dosing eCRF:

- **Number of infusions:** number of administered, nonzero infusions of daratumumab.
- **Average dose (mg):** total actual daratumumab dose (mg) divided by the number of infusions of daratumumab.
- **Dose administered per cycle (mg):** the actual dose of daratumumab administered (mg) per cycle.

6.5. Study Drug Compliance

For participants in the FAS, overall compliance (%) for INCB001158 will be calculated as follows:

$$\text{overall compliance (\%)} = 100 \times [\text{total dose actually taken}] / [\text{total prescribed dose}].$$

The total prescribed dose is defined as the sum of the doses prescribed by the investigator, accounting for dose modifications.

The total actual dose taken will be calculated based on information entered on the Drug Accountability eCRF. If there are dispensed drugs that have not been returned yet, the actual dose taken starting from the dispense date of the unreturned drugs will be imputed by the dose taken as reported on the Dose INCB001158 eCRF.

6.6. Prior and Concomitant Medication

Prior medications and concomitant medications will be coded using the WHO Drug Dictionary. The number and percentage of participants in the FAS for each prior and concomitant medication will be summarized by WHO drug class and PT.

A listing of post-treatment anticancer treatments will also be provided.

7. EFFICACY

[Appendix A](#) provides a list of data displays. Sample data displays are included in a separate document.

7.1. General Considerations

The primary endpoint of the Phase 2 portion of the Protocol is ORR, defined as the proportion of participants with CR, VGPR, or PR, according to IMWG criteria in the randomized FAS. Due to the small sample size of participants enrolled in Phase 2 at the time of study termination, only listings of the efficacy data will be provided.

7.2. Efficacy Hypotheses

As a result of an early-termination decision following a recruitment challenge (no safety-related concerns), efficacy analyses will not be performed due to an insufficient number of participants enrolled in Phase 2. Listings of the efficacy data will be provided for participants in Phase 1 and Phase 2. Details of the efficacy hypotheses may be found in the Protocol.

